6.2 RANDOMIZATION STRATEGY

Covariate-based constrained randomization⁹⁸ may be used to enhance study arm balance on key factors during randomization of the clinics in this cluster-randomized trial. This method permits the use of multiple balance factors and can yield improved study arm balance and increased statistical power beyond simple randomization when balance factors are included in both the design and analysis phase⁹⁹ of the study. Clinic-level attributes of clinics and patient mix to be used as balance factors will be obtained via EHR data and ascertained for care in clinics in the 18 months prior to randomization. Proposed clinic-level balance factors include baseline levels of BP re-measurement and HTN recognition, number of visits with patients age 6-17 (ranging from 145 to 6556 patients per clinic over 18 months in preparatory data), location (metropolitan/micropolitan (20 clinics) versus small town/rural (25 clinics)), and proportion of public pay patients (ranging from 13% to 73%). Randomization will be carried out with the CCR macro for use within SAS¹⁰⁰, and conducted one month prior to implementation of the low- and high-intensity strategies in clinics.

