The dependent variable for Aim 1 (BP_Remeasure) is a binary indicator of post-implementation re-measurement of BP at the index visit at which the elevated BP occurred. For H1 this endpoint will be predicted by a fixed effect study arm term (TeenBP_j) contrasting low- plus high-intensity PedsBP clinics with usual care clinics, stratification factors used in the clinic randomization (StratFactors_j), and patient-level covariates of age, sex, and SBP percentile of the elevated BP. A random intercept for clinics is included (u_{j0}) to account for the clinic-level randomization. The analysis for H2 will contrast high- and low-intensity clinics (HighVsLow_j) and exclude usual care clinics from the analysis, but otherwise be similar to H1. Statistically significant study arm contrasts (alpha=.05) and parameters in the expected direction will support the H1 and H2 predictions stated for Aim 1.

Hypotheses 3 and 4 for **Aim 2** posit that patients who newly meet HTN criteria at clinics with low- or high-intensity PedsBP CDS will be more likely to have their HTN recognized within 6 months as compared to patients seen at usual care clinics, and that recognition of HTN will be more likely for patients seen at high-intensity rather than low-intensity clinics. Generalized linear mixed-model regression with a logit link and binomial error distribution may be used to test the effect of the interventions following the same analytic strategy and equations for H1 and H3 above, with the substitution of HTN recognition as an endpoint in place of BP re-measurement, and the use of patient-level covariates of the lowest SBP percentile at the index visit, and BMI percentile at the index visit. Study arm contrasts will test differences in BP recognition for CDS (low-intensity or high-intensity) vs. Usual care and high-intensity vs. low-intensity. Statistically significant study arm contrasts (alpha=.05) and parameters in the expected direction will support the H3 and H4 predictions stated for Aim 2.

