11 APPENDIX 1 – ASSESSMENT OF RISK FACTORS

Assessment of Cardiometabolic Disease Risk Factors and Health-Related Social Needs in Pediatric Patients with and without IDD

Background and Rationale:

Cardiometabolic risk in childhood and adolescence is associated with future disease and cardiovascular mortality^{1,2,3}. Although precise definitions and cut-offs may vary, cardiometabolic and cardiovascular disease (CVD) risk in childhood and adolescence can be measured across five domains (blood pressure (BP), lipids, glucose/Hgb A1c, smoking, body mass index (BMI)). Of these, BP and BMI are routinely assessed at all pediatric primary care visits, smoking status may be assessed during adolescent well visits, and lipids and glucose/Hgb A1c may only be assessed in patients with obesity or other risk factors^{4,5,6}.

People with Intellectual and Developmental Disabilities (IDD) have higher rates of cardiometabolic risk factors and cardiovascular disease compared to similar patients without IDD^{7,8}. There is evidence that this risk begins to accumulate in childhood, but there is a lack of data describing the prevalence of CVD risk factors in pediatric patient populations with IDD. In order to learn how to better serve pediatric patients with IDD and their families and prolong length and quality of life for individuals with IDD, better data on risk factors and areas for potential risk modification are needed.

Essentia Health started routinely collecting data on patients' health-related social needs (HRSN) in 2020 in all primary care visits. This includes personal and medical transportation, food scarcity and food insecurity, and financial strain aimed to identify those report any adverse social conditions that can contribute to poor health^{9,10,11}. Prior studies have noted an association between CVD risk and HRSN¹².

The PedsBP clinical decision support (CDS) tool has potential to improve BP measurement, remeasurement and control, as well as raise awareness of CVD risk factors and work up for secondary causes¹³. Assessment of HRSN routinely occurs in primary care clinics and association of HRSN and CVD risk factors is important to describe.

This cross-sectional analysis utilizes the baseline data from patients' PedsBP CDS index visit obtained from web service call data that is gathered at the index visit, as well as historical data prior to the index visit that will be gathered from the EHR.

Aims:

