1. In youth 6-17 years of age, describe the assessment of CVD risk factor and HRSN data in the EHR by:
 - a. rural vs urban dwelling
 - b. male vs female sex
 - c. IDD vs non-IDD
2. In youth 6-17 years of age with CVD risk factor and HRSN assessment in the EHR, describe the prevalence of CVD risk factors and HRSN:
 - a. rural vs urban dwelling
 - b. male vs female sex
3. Describe the association of CVD risk factors and HRSN.
4. Determine the prevalence of having one or more- cardiometabolic risk factors among a cohort of pediatric patients 6-17 years receiving care in a large, primarily rural health system with a diagnosis of IDD (as defined by

ICD-10 diagnostic codes for IDD). Compare this prevalence with that of patients of similar age in the health system without IDD diagnosis.

Hypotheses:

1. Comparing study-eligible pediatric patients on the assessment of CVD risk factor and HRSN data:
 - a. Assessment of CVD risk factors and HSRN will be more complete in urban-dwelling than rural-dwelling pediatric patients.
 - b. Assessment of CVD risk factors and HSRN will be more complete in female than male pediatric patients.
 - c. Assessment of CVD risk factors and HSRN will be more complete in patients with IDD than patients without IDD.
2. Comparing study-eligible pediatric patients on the prevalence of CVD risk factors and HRSN:
 - a. Rural pediatric patients will have a higher prevalence of CVD risk factors and HRSN than urban pediatric patients.
 - b. Male pediatric patients will have a higher prevalence of CVD risk factors and HRSN than female pediatric patients.
3. Patients with a higher count of HRSN will be more likely to have any CV risk factors.
4. Among those with at least two documented cardiometabolic risk measures, those with IDD will have increased CVD risk, compared with those with no IDD diagnosis.

Population: All PedsBP study-eligible patients aged 6-17 years on the date of a potential index visit (first visit) at a randomized Essentia Health clinic between August 1, 2022, to July 31, 2023.

Exclusion Criteria: Opted out of use of their data for research prior to performing analyses.

Informed Consent: See Section 9.1.1 above.

Main Measures: A complete list of variables that will be collected can be found in the data dictionary (separate document located in the study file).

Variable	Description	Data Source
Patient Description	Age, sex, race, ethnicity, vitals, labs, medications, diagnoses, encounters	CDS, EHR Clarity

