Provider Type and Specialty	Standard categories	EHR Clarity
Tobacco and Marijuana Status	Standard categories	EHR Clarity
Rural-urban commuting area (RUCA)	Ruca, zip code(s)	EHR Clarity
Intellectual and Developmental Disabilities (IDD)	Autism spectrum disorder, intellectual disability, cerebral palsy, genetic conditions, child disintegrative disorder, fetal alcohol syndrome	EHR Clarity
Health-Related Social Needs (HRSN)	Personal transportation, medical transportation, food scarcity, food insecurity, and financial strain	EHR Clarity

Analysis Plan:

Aim 1: Describe the assessment of CVD risk factor and HRSN data in the EHR by urban vs. rural patient dwelling, patient sex, IDD vs. non-IDD status.

The count and percentage of patients having assessment in the EHR will be computed for: a) assessment of information needed to document each individual CVD risk factor in the EHR (e.g., BP measured at the index visit, lipids measured ever, glucose or A1c measured ever, smoking assessed in the past 2 years, BMI recorded in the past 2 years, problem list diagnosis of any CVD risk factor), b) documentation of any HRSN in the EHR. These summaries will be computed for all patients and stratified individually and multiply by patient dwelling (rural, urban), patient sex, patient age group. Differences in assessment of information (0/1) for each assessment will be assessed with logistic regression analysis predicting assessment of information from patient factors used as stratification variables.

The same analysis strategy will be used to describe and test assessment of CVD risk factor information and HRSN for patients with IDD vs. non-IDD.

Aim 2. Describe the prevalence of CVD risk factors and HRSN by urban vs. rural patient dwelling, patient sex.

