The prevalence of CVD risk factors will be computed as: a) the prevalence of any risk factor among the five of interest, and b) the prevalence of each individual risk factor. HRSN prevalence will be computed as the presence of any HRSN present. These summaries will be computed for all patients having CVD risk factor assessment (and HRSN assessment) from Aim 1 and stratified individually and multiply by patient dwelling (rural, urban), patient sex, patient age group. Differences in prevalence as defined above will be assessed with logistic regression analysis predicting prevalence from patient factors used as stratification variables. In addition, multiple linear regression will be used to assess the association of count of CVD risk factors with patient factors. Models will include the stratification factors listed above.

Aim 3. Describe the association of CVD risk factors and HRSN.

The association of any CVD risk factor (0/1) with presence of HRSN (0/1) overall and stratified individually and multiply by patient dwelling, patient sex, patient age group will be assessed in contingency table analysis and tested via Pearson and Cochran-Mantel-Haenszel chi-square tests. The association of each CVD risk factor with presence of HRSN (0/1) will be addressed with the same approach.

Multiple linear regression will be used to assess the association of count of CVD risk factors with presence of HRSN (0/1). Models will include the stratification factors listed above. One set of models will exclude any interactions and a second set will include interactions in order to formally test for differences in the association of count of CVD risk factor and HRSN by subgroups (e.g., patient age group).

Aim 4. Describe the prevalence of having one or more CVD risk factors in patients with a diagnosis of IDD vs. no diagnosis.

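### Appendix 1 tests rural versus urban dwelling with models that ignore clinic clustering, so hypotheses 1a and 2a are likely to be rejected too often

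*Combined protocol and SAP*

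**What the plan says.** Appendix 1 analyses study-eligible patients aged 6 to 17 whose first visit to a randomized clinic fell in a 12-month window. Two of its hypotheses concern dwelling and are directional:

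- 1a: "Assessment of CVD risk factors and HSRN will be more complete in urban-dwelling than rural-dwelling pediatric patients".
- 2a: "Rural pediatric patients will have a higher prevalence of CVD risk factors and HRSN than urban pediatric patients".

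For Aim 1, differences in assessment "will be assessed with logistic regression analysis predicting assessment of information from patient factors used as stratification variables". For Aim 2 the method is "logistic regression analysis predicting prevalence from patient factors used as stratification variables", with a linear regression of the risk-factor count. For Aim 3, associations with health-related social needs (HRSN) are "tested via Pearson and Cochran-Mantel-Haenszel chi-square tests", again with a linear model for the count. Aim 4 repeats the Aim 2 approach for intellectual and developmental disability (IDD). The predictors are all patient characteristics.

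The trial models in Section 8.4 differ: "A random intercept for clinics is included", to reflect randomization by clinic. Appendix 1 does not refer to that model, although it does point back to Section 9.1.1 on consent.

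**The concern.** Patients of one clinic share staff, workflow and catchment, so their outcomes are correlated. An ordinary regression treats them as independent. For a covariate balanced within clinics, such as sex, this does little harm. For a covariate that is concentrated in particular clinics, the standard error is too small.

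Dwelling is likely to be of the second kind. It is derived from each patient's RUCA code or zip code, but Section 6.2 divides the clinics themselves into 20 metropolitan/micropolitan and 25 small town/rural. The documents also make outcome variation between clinics credible. Section 5 shows different staffing models, Section 6.2 gives a public-pay share of 13% to 73%, and Section 8.2 uses clinic ICCs of 0.03 and 0.035 for related care processes.

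At stake is whether a significant result for 1a or 2a reflects where children live or only which clinics they happen to attend.

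**Working it through.** **The plan's own figures.** Appendix 1 states no sample size, power or alpha. The nearest stated figure is H1 in Section 8.2: 161 patients per clinic, ICC 0.03, 15 versus 30 clinics, 30% versus 38%, 80% power. The design effect is 1 + 160 × 0.03 = 5.8. Effective sizes are 15 × 161 / 5.8 = 416 and 30 × 161 / 5.8 = 833, and a pooled two-sided z test has about 80% power. This agrees, so the main trial allows for clustering correctly.

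**Inputs for Appendix 1**

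- Patients per clinic, Aim 1: 44,061 over 18 months (Section 8.2) × 12/18 = 29,374; divided by 45 clinics, about 653. The pro-rating is an assumption.
- Patients per clinic where laboratory results are needed: the appendix says lipids and glucose "may only be assessed in patients with obesity or other risk factors". If only the 15% with obesity (Section 5) have them, 653 × 0.15 = about 98. This is an assumption.
- Outcome ICC: 0.03, borrowed from BP re-measurement (Section 8.2), and 0.01 as a lower value. Both are assumptions for these outcomes.
- Share of dwelling variance lying between clinics, ρ: not in the documents, so varied.
- Test: two-sided 5%, as in Section 8.

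**Design effect.** DE = 1 + (m − 1) × ICC × ρ. The ordinary standard error is too small by √DE.

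| m | ICC | ρ = 10%: DE, √DE | ρ = 50%: DE, √DE |
|---|---|---|---|
| 653 | 0.03 | 2.96, 1.7 | 10.78, 3.3 |
| 653 | 0.01 | 1.65, 1.3 | 4.26, 2.1 |
| 98 | 0.03 | 1.29, 1.1 | 2.46, 1.6 |
| 98 | 0.01 | 1.10, 1.05 | 1.48, 1.2 |

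**From dwelling mix to ρ.** Suppose a fraction a of patients at the 25 rural clinics and b at the 20 urban clinics live rurally. With equal clinics the overall fraction is p = (25a + 20b)/45, and ρ = (a − b)² × 25 × 20 / 45² ÷ [p(1 − p)].

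- 90% / 10%: p = 0.544, ρ = 0.158 / 0.248 = 64%.
- 80% / 30%: p = 0.578, ρ = 0.0617 / 0.244 = 25%.
- 65% / 45%: p = 0.561, ρ = 0.0099 / 0.246 = 4%.

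**Type I error, closed form.** 2 × [1 − Φ(1.96/√DE)]. At m = 653 and ICC 0.03, the three splits give DE = 13.5, 5.9 and 1.8, hence 59%, 42% and 14%.

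**Type I error, simulated.** 4,000 runs, 45 clinics, beta-binomial outcome at 30%, no true dwelling effect, ordinary Wald test. Cells are for the 90/10, 80/30 and 65/45 splits.

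| m, ICC | Equal clinics | Unequal clinics (CV 0.99) |
|---|---|---|
| 653, 0.03 | 59%, 43%, 14% | 69%, 54%, 21% |
| 653, 0.01 | 39%, 24%, 8% | 50%, 31%, 11% |
| 98, 0.03 | 25%, 14%, 7% | 35%, 20%, 8% |
| 98, 0.01 | 12%, 8%, 6% | 17%, 10%, 6% |

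The unequal sizes at a mean of 653 were log-normal, from 57 to 3,475. Section 6.2 reports clinics "ranging from 145 to 6556 patients per clinic over 18 months in preparatory data", which pro-rates to 97 to 4,371, so the match is approximate.

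A separate simulation used a random clinic effect on the log-odds scale, ICC 0.03 and unequal clinics. Splits of 90/10, 80/20, 65/35 and 55/45 gave 59%, 50%, 28% and 9%.

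**Other covariates, equal clinics.** Sex: about 5%. IDD: 5% to 7% (assumed 5% prevalence, covariate ICC 0.01). HRSN: 5% to 16% (assumed 15% prevalence, covariate ICC 0.05).

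**Does a clustered analysis repair it?** A delete-one-clinic jackknife variance with a t reference on 43 degrees of freedom gave 4.1% to 5.9% in all 24 dwelling scenarios; a repeat gave 4.7% to 6.3%. A sandwich variance with only a simple scaling factor reached 8.2% with unequal clinics. In the separate simulation at ICC 0.03, ordinary cluster-robust errors gave 6% to 10%. The correction therefore needs to be named.

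**The case against.** The strongest reply is that the analysis is ancillary and largely descriptive, and that it covers all eligible patients at these clinics, not a sample of clinics. If the target is the rural-urban difference among exactly these patients, clinic differences that follow dwelling are part of that difference, and a rejection is not a false positive. This reading does not fit the text. Hypotheses 1a and 2a are worded generally and are tested with models that yield p-values. Those p-values make sense only if the result is meant to reach beyond the patients in hand.

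The second reply is that every input driving the size is assumed. The ICC of 0.03 comes from a staff-behaviour outcome in another health system, the dwelling splits are scenarios, and the appendix gives no rural cut-point. That stands. At an ICC of 0.001 with 653 per clinic, the closed form gives only 6% at ρ = 10% and 13% at ρ = 100%.

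Some outcomes are also poorly represented. A recorded BP is an eligibility condition, so its assessment is almost constant. The figure of 98 per clinic fits only laboratory measures, and 15% is not a firm bound on who is tested. The 30% outcome rate is also assumed. These points narrow the concern to lipid, glucose, smoking and HRSN assessment and to prevalence.

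Finally, the evidence is strong for dwelling, moderate for HRSN and weak for IDD and sex. That also stands, but one common method for all four aims costs almost nothing.

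**Conclusion.** The concern holds. As written, the Appendix 1 models give standard errors for dwelling that are too small whenever dwelling and outcome both vary by clinic. The direction is firm unless dwelling is nearly unrelated to clinic or the outcome ICC is close to zero. The size is not firm: across the simulated 90/10, 80/30 and 65/45 scenarios, a nominal 5% test rejects in 6% to 69% of null trials, depending on assumed ICC, dwelling mix, clinic size and its spread.

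The effect is confined mainly to hypotheses 1a and 2a, with a possible moderate effect on hypothesis 3. Counts, percentages and prevalences do not change, and H1 to H4 are unaffected. It should be fixed before the Appendix 1 tests are reported; confidence is medium because the documents do not supply the deciding inputs.

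**What to change.** In the Appendix 1 Analysis Plan, state for Aims 1 to 4 that all tests account for clustering by index-visit clinic. Use GEE, or the planned logistic and linear models with clinic-robust standard errors, and name a small-sample bias correction (jackknife or Mancl-DeRouen type) and a t reference. This keeps the overall population difference as the target, which the appendix should say. A clinic random intercept, as in Section 8.4, is suitable only if a clinic-conditional effect is wanted.

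Keep the Aim 3 contingency tables as description, and base the HRSN tests on the same clustered models instead of unadjusted Pearson and Cochran-Mantel-Haenszel tests.

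The cost is one or two sentences. The index-visit clinic is already known because it determines the study arm (Section 6.1.1), so no new data are needed. P-values for dwelling will generally become less favourable.

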The prevalence of CVD risk factors will be computed as: a) the prevalence of any risk factor among the five of interest, and b) the prevalence of each individual risk factor. HRSN prevalence will be computed as the presence of any HRSN present. These summaries will be computed for all patients having CVD risk factor assessment (and HRSN assessment) from Aim 1, and multiply stratified by IDD vs. non-IDD and patient age group. Differences in prevalence as defined above will be assessed with logistic regression analysis predicting prevalence from IDD vs. non-IDD and patient factors used as stratification variables. In addition, multiple linear regression will be used to assess the association of count of CVD risk factors with IDD vs. non-IDD and patient factors.

References

1. Jacobs DR, Jr., Woo JG, Sinaiko AR, et al. Childhood Cardiovascular Risk Factors and Adult Cardiovascular Events. *N Engl J Med.* May 19 2022;386(20):1877-1888. doi:10.1056/NEJMoa2109191

6. Hagan, J. F., Shaw, J. S., & Duncan, P. M. (2017). Bright futures: Guidelines for health supervision of infants, children, and adolescents: Pocket guide. American Academy of Pediatrics/Bright Futures, 2017. APA, 7th ed.

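### Appendix 1 compares an any-of-five outcome and a factor count across groups it expects to be assessed unequally, with no rule for unmeasured factors, so testing alone can create or hide differences

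*Combined protocol and SAP*

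**What the plan says.** All of this is in the Combined protocol and SAP, section 11 (Appendix 1).

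- **Background and Rationale.** Risk is measured in five domains: BP, lipids, glucose/A1c, smoking and BMI. BP and BMI are described as routine at every visit and smoking as something that may be asked at adolescent well visits, while "lipids and glucose/Hgb A1c may only be assessed in patients with obesity or other risk factors".
- **Hypothesis 1.** "Assessment of CVD risk factors and HSRN will be more complete in urban-dwelling than rural-dwelling pediatric patients"; "Assessment of CVD risk factors and HSRN will be more complete in female than male pediatric patients"; "Assessment of CVD risk factors and HSRN will be more complete in patients with IDD than patients without IDD".
- **Hypotheses 2 and 4.** Prevalence is predicted to be higher in rural than urban patients (2a), in males than females (2b), and in patients with IDD than without (4). Hypothesis 4 alone sets a floor of two documented risk measures.
- **Analysis Plan, Aim 2.** The outcomes are "the prevalence of any risk factor among the five of interest" and each factor singly, analysed by logistic regression. In addition, "multiple linear regression will be used to assess the association of count of CVD risk factors with patient factors".
- **Analysis Plan, Aim 4.** The same outcomes are used, and "multiple linear regression will be used to assess the association of count of CVD risk factors with IDD vs. non-IDD". The two-measure floor is not repeated.

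Under both aims the denominator is patients who have had risk factor assessment as described under Aim 1. Aim 1 describes assessment factor by factor, with look-back periods that differ by factor.

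**The concern.** A yes/no outcome for any of five factors, and a count of factors, can record only what was looked for. If one group has more factors measured, it has more chances to show one. Here the plan itself predicts unequal measurement in the groups whose prevalence it then compares.

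The direction differs by hypothesis. For IDD, the group expected to be better assessed is also the group expected to have more risk, so the artefact runs with hypothesis 4 and invites a false positive. For dwelling and sex, the better-assessed groups (urban, female) are those expected to have less risk, so the artefact runs against hypotheses 2a and 2b and could mask or reverse a true difference.

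The floor in hypothesis 4 gives little protection. Routine BP plus BMI would satisfy it for nearly everyone, so the difference between two and five factors measured remains.

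**Working it through.** **The plan's own figure.** Appendix 1 gives no sample size, prevalence or testing rate, so there is nothing to reproduce. What follows is an illustration.

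**Step 1: readings of the denominator.**
- Any factor, or at least two, assessed: unmeasured factors cannot contribute, so both outcomes depend on how much was measured.
- All five assessed: testing is equal, but the sample is restricted to patients who had laboratory tests, and the Background says these may be patients with obesity or other risk factors.

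**Step 2: inputs for the first reading.**
- Obesity 15% (section 5, Study Population) and elevated first BP 16% (section 8.2), both taken as measured in everyone.
- Assumed: prevalence of lipid, glucose and smoking factors; share tested in each group; independence of factors; identical true prevalence in both groups; untested scored as no factor.

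**Step 3: formulas.** With t the share tested and p the true prevalence of each factor:
- P(any) = 1 − product of (1 − t × p)
- expected count = sum of (t × p)

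Middle case, less-tested group: 1 − 0.85 × 0.84 × (1 − 0.10 × 0.10) × (1 − 0.10 × 0.05) × (1 − 0.50 × 0.05) = 1 − 0.714 × 0.99 × 0.995 × 0.975 = 0.314. Better-tested group: 1 − 0.714 × 0.96 × 0.98 × 0.975 = 0.345. Counts: 0.15 + 0.16 + 0.10 × 0.15 + 0.50 × 0.05 = 0.350 and 0.31 + 0.40 × 0.15 + 0.025 = 0.395.

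| Case | Lipids / glucose / smoking prevalence | Labs tested | Smoking assessed | Any factor | Gap (points) | Odds ratio | Count gap |
|---|---|---|---|---|---|---|---|
| Low | 5 / 2 / 3% | 10% vs 20% | 50% in both | 30.2% vs 30.7% | 0.5 | 1.02 | 0.007 |
| Middle | 10 / 5 / 5% | 10% vs 40% | 50% in both | 31.4% vs 34.5% | 3.1 | 1.15 | 0.045 |
| High | 20 / 10 / 5% | 10% vs 40% | 40% vs 70% | 32.1% vs 39.1% | 7.0 | 1.36 | 0.105 |

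If both groups are tested to the same extent, every gap is exactly zero.

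**Step 4: would it be declared significant?** Scaling the 44,061 patients expected over 18 months (section 5) to the appendix's 12-month window gives 44,061 × 12/18 = 29,374, an assumption. With a two-sided 0.05 test of two proportions, the chance of a false significant any-factor difference is 15%, about 100% and about 100% for the three cases with equal groups. If one group is 5% of patients, it is 6%, 69% and about 100%.

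**Step 5: laboratory tests only in obese patients.** These patients already count through BMI, so any-factor prevalence from BP, BMI and laboratory factors stays at 1 − 0.85 × 0.84 = 28.6% in both groups. Only the count moves, by 0.15 × (difference in testing) × (summed laboratory prevalence in the obese). With 30% vs 60% tested and 25% summed prevalence, that is 0.15 × 0.30 × 0.25 = 0.011. With 20% vs 60% and 55%, it is 0.15 × 0.40 × 0.55 = 0.033.

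**Step 6: the all-five reading.** Take one laboratory factor at 8% in non-obese patients, 60% of obese patients tested, and 5% of non-obese tested. Any-factor prevalence among the non-obese is 1 − 0.84 × 0.92 = 0.227. Among the tested it is (0.15 × 0.60 + 0.85 × 0.05 × 0.227) / (0.15 × 0.60 + 0.85 × 0.05) = 75%. With 30% of non-obese tested it is 43%. In the whole population it is 0.15 + 0.85 × 0.227 = 34%.

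**The case against.** Several objections have force.

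- **Scoring is not stated.** A reader might infer that an unmeasured factor is counted as absent. The text never says so. The denominator is limited to assessed patients, and the appendix refers variables to a separate data dictionary that may hold a rule. This stands: the supported claim is that the analysis plan leaves both the denominator and the scoring open. It does not clear the plan, because each reading in Step 1 carries a bias.
- **Size.** A reader might infer that testing is bound to produce a large gap. Suppose each patient has either two or five factors measured, each factor has 10% prevalence, and all five are measured in 60% vs 30%. The result is 32.2% vs 25.6%, a gap of 6.6 points. That is near the top of the range above and rests on testing rates the documents do not give. If only smoking assessment differed, by 30 points at an assumed 5% prevalence, the gap would be 0.84 × 0.85 × 0.05 × 0.30 = 1.1 points.
- **Testing by indication.** A reader might infer that it makes the any-factor bias worse. The documents do not support that. Where obesity is the indication, Step 5 shows the laboratory part is zero. Indications outside the five domains could still add bias, so the direction is unknown.
- **Existing safeguards.** Aim 1 reports assessment by these same groups, single-factor prevalence is already planned, and the Aim 2 models include age group. These make unequal testing visible and absorb some age-driven smoking assessment. They do not correct the any-factor or count comparisons.

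**Conclusion.** The concern holds in a bounded form. The appendix compares two outcomes that can depend on how much was measured, across groups it expects to be measured unequally, without a denominator rule, a scoring rule or adjustment for the number of factors assessed. The spurious any-factor gap is about 0.5 to 7 points under the stated assumptions. It can be near zero if laboratory testing is confined to obese patients and smoking is assessed equally. In a sample of this size, gaps in the middle of the range could well be reported as findings, so conclusions on hypotheses 2a, 2b and 4 could partly reflect testing practice. The documents do not show that they would do so entirely. Only the cross-sectional Appendix 1 analyses are affected; the trial's primary and secondary outcomes are not.

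**What to change.** 1. State one denominator and one scoring rule for unmeasured factors, and apply both to Aims 2, 3 and 4. Either carry hypothesis 4's floor into the Aim 4 analysis text or replace it with the common rule.
2. Base the main between-group any-factor and count comparisons on BP and BMI, which the appendix calls routine. State how a missing BMI is handled: CDS eligibility in section 5.1 requires a BP, although sections 1.1 and 5 describe a population with height and weight recorded.
3. Report lipids, glucose/A1c and smoking singly among those tested, noting that selective testing remains.
4. Give the five-factor any-factor and count results as sensitivity analyses, adjusted or stratified for number of factors assessed, or weighted for the probability of testing. Label any analysis restricted to patients with all five measured as a selected sample; Step 6 shows it is not a clean remedy.

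The cost is appendix wording and recoding of two outcome variables. The real loss is that the main composite covers two domains rather than five. If the sponsor prefers to keep five domains as the main outcome, items 1 and 4 are the minimum.
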